4 STUDY DESIGN

4.1 OVERALL DESIGN

Description of the Study Design

To address aims 1 and 2, we plan to use a two-arm, two-stage randomized trial design of 632 patients with HIV who smoke cigarettes and receive their HIV care in one of three health systems.

To address aim 3, we plan to hold pre- and post-trial surveys involving clinicians, staff, clinical leadership, social workers, psychologists, and care coordinators to conduct an implementation focused-evaluation of a clinical pharmacist-delivered intervention.

Description of Procedures Being Performed

For aims 1 and 2, at baseline, intake history, demographics, questionnaires relating to depression, drug and alcohol problems, smoking habits, medication adherence, HIV symptoms and quality of life will be performed. The depression, substance use, quality of life questionnaires, HIV symptom index and costs related to tobacco use and clinic travel will be administered at weeks 12 and 24. Tobacco measures will be performed at all time points - relating to carbon monoxide levels, cigarette consumption, nicotine dependence, tobacco use and e-cigarette use. HIV related measures pertaining to CD4 count, viral load and other lab values, health care utilization (ED visits, hospitalizations), and treatment services to address tobacco use will be collected at baseline, week 24 and month 12. Patient satisfaction, opinions about services and adherence will also be recorded. At baseline, participants will be randomized 1:1 to either NRT (nicotine replacement therapy) or NRT + CM. Participants will receive a prescription for 12 weeks of the long-acting NRT patches and short-acting NRT (i.e., gum, lozenges, an inhaler or spray) with standard advice. Participants will fill the prescription through their usual pharmacy of choice.

Participants will be invited to complete five follow-up visits with the clinical pharmacist over the following 12 weeks to address medication adherence, side effects and review progress in achieving smoking abstinence. For those randomized to additionally receive contingency management (CM), these visits will be integrated into the sessions with the clinical pharmacist. At week 12, participants who responded to initial treatment will continue without change. Participants who do not respond to the intervention, will be re-randomized, to switch to either VAR or bupropion or intensify to CM+.

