Participants will be invited to return to visit the clinical pharmacist for an additional 5 visits, with the final visit at week 24. All of the CM sessions will be audio recorded and reviewed to ensure compliance with management strategies. NRT only sessions will also be recorded and a random sample (10-20%) will be reviewed to also ensure fidelity to the protocol and to provide feedback to the clinical pharmacists. No video recording will occur. [name], the CM consultant on the project, will be primarily responsible for reviewing the recordings. The audio files will be sent to the Coordinating Center via the Yale OneDrivesystem, which encrypts the recordings. The files will not contain names or other identifying information. The audio files will be stored on Yale Secure Box; only [name], [name], and [name] will have access to the folder. A random sample of the audio files may be transcribed via professional transcription services to allow for qualitative analysis. The recordings will be destroyed after 6 years.

For aim 3, all clinicians, staff, clinical leadership, social workers, psychologists, and care coordinators employed at the participating site will be invited to complete the brief surveys pre- and post- trial intervention, administered through REDCap and distributed via email. The survey will assess knowledge, attitudes and practices that may impact implementation of a clinical pharmacist delivered intervention involving medications and CM and will be modeled after the ORIC and CMBQ and other surveys.

To maintain safety procedures, in some circumstances, patients can participate in study activities/counseling, and undergo surveys and be consented for the study, via video conferencing link or phone. Patients will be given a link to video conference with provider/clinical pharmacist/coordinator to maintain social distancing guidelines. Zoom version provided is HIPAA compliant per Sinai. Or if using phone for study procedures, patients will be contacted via the phone number they provided.

Description of the Source Records that Will Be Used to Collect Data About Subjects

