6.4 STUDY INTERVENTION COMPLIANCE

Study intervention compliance will be recorded in REDCap based on self-reported information of medication and compliance will be measured based on participants showing up to pharmacy visits which will also be recorded on REDCap.

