9.4.8 EXPLORATORY ANALYSES

Exploratory Analysis. We will determine the overall best strategy with regard to 24-week abstinence. There are four strategies to compare: 1) NRT followed by VAR or bupropion in non-responders; 2) NRT followed by NRT+CM in non-responders; 3) NRT+CM followed by VAR or bupropion+CM in non-responders; 4) NRT+CM followed by NRT+CM+ in non-responders. Choosing the optimal strategy is an estimation rather than hypothesis testing problem. Weighted logistic regression will be used to estimate 24-week abstinence rates for each of the strategies. Inverse probability weighting will account for non-

responders being re-randomized and thus split in two groups as they will be underrepresented relative to responders. The analysis will include parameters for the initial randomization group as well as site, age, gender and HSI as baseline covariates. Predicted probabilities and 95% confidence intervals will be estimated for each of the strategies. The strategy with the highest predicted probability will be identified as the optimal strategy.

We will additionally examine "dose response effects" and examine the impact of number of completed interventions sessions as measure of intensity of intervention on outcomes.⁷

We will conduct exploratory analyses by subgroups (see 9.4.6).

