10.1.10 PROTOCOL DEVIATIONS

Documenting Protocol Deviations

Medications:

If a participant does not receive the medications as part of their assigned treatment arm, this should be documented as a protocol deviation in REDCap. This may be entered once in the Protocol Deviation Form in the Baseline Forms, Week 12 Forms, Week 24 Forms, or Unscheduled Visit Forms.

This may occur for various reasons: 1) participant declines a particular medication; 2) participant did not fill a prescription for any reason; 3) incorrect medication was prescribed.

NRT: Participants should be prescribed both a long- and short-acting nicotine replacement therapy in Stage 1. If one or both were not acquired, then one protocol deviation should be submitted.

VAR: If varenicline or bupropion was not acquired when a participant was randomized to either the VAR or VAR+CM arm in Stage 2, then one protocol deviation should be submitted.

These deviations are not meant to be punitive in nature. Rather, we need a way to be able to track how often this is happening. (Medications actually taken will also be tracked via the Smoking Related Treatment Services Form)

Incorrect CM draws:

If participant is awarded an incorrect number of draws from the fishbowl, this needs to be documented as a protocol deviation.

Some examples may be:

- a) Participant was awarded more than the maximum number of draws:
Maximum is 9 draws for the NRT+CM intensified group
Maximum is 5 draws for all other groups

- b) Participant was awarded draws, even if they reported smoking (even a puff) in the last 7 days.
Reminder: Smokerlyzer should ONLY be used to confirm a verbal report of no smoking in the past 7 days. Draws are then awarded if eCO <= 6ppm.

- c) Too many or too few draws per specific CM visit.

We will not report medication deviations related to medication non-use and incorrect CM draws (described in the above sections) as individual events to the Mount Sinai IRB to limit administrative burden as they are not indicators of human subject risk. Instead, we will present these data as aggregate to our DSMB and in our annual report.

It is the responsibility of the site Principal Investigator to use continuous vigilance to identify and report deviations within 5 working days of identification of the protocol deviation, or within 5 working days of

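### The exploratory session-count analysis in section 9.4.8 is worded as dose response and impact, but it can show only an association with attendance

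*Combined protocol and SAP*

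**What the plan says.** Section 9.4.8 (Exploratory Analyses) states that the team will look for dose response and "examine the impact of number of completed interventions sessions as measure of intensity of intervention on outcomes". For this item it gives no model, outcome, time point, covariates, significance level or rule on which sessions count.

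The rest of the protocol determines what a session count would measure:

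- **Visits offered.** Section 4.1, stage 1: "Participants will be invited to complete five follow-up visits with the clinical pharmacist over the following 12 weeks". For participants also assigned to CM, "these visits will be integrated into the sessions with the clinical pharmacist". Stage 2: "Participants will be invited to return to visit the clinical pharmacist for an additional 5 visits", the last at week 24. The number of visits offered does not differ by arm.
- **Who is paid.** Section 10.1.10 lists this as a protocol deviation: "Participant was awarded draws, even if they reported smoking (even a puff) in the last 7 days". It also sets a breath-test condition: "Draws are then awarded if eCO <= 6ppm".
- **Missed visits.** Under section 1.3, if COVID-19 restrictions prevent a CM visit and remote testing is unavailable, an informant's attestation of seven smoke-free days is accepted as a successful CM visit.
- **Compliance.** Section 6.4: "compliance will be measured based on participants showing up to pharmacy visits".

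**The concern.** Impact and dose response are causal terms, but the exposure is attendance, which participants select after randomization. Three routes can link it to smoking even if sessions do nothing.

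1. **Abstinence raises attendance.** At a CM visit an abstinent participant can earn draws and a smoking participant cannot. This is reverse causation, and baseline covariates cannot remove it.
2. **Abstinence enters the count directly.** An unattended visit can be credited because an informant attests abstinence.
3. **A shared cause.** Motivated participants may both attend more and smoke less, in either arm.

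Timing is also open. Nothing limits the count to sessions before the outcome, and the final visit falls in the same week as the 24-week assessment.

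At stake is a possible statement that each extra session reduces smoking, made in a trial whose randomized comparisons might show nothing of the kind.

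**Working it through.** **Step 1. Reproduce the plan's nearest figure.** The plan gives no figure for this analysis, so the check is on the section 9.2 design used below. With SD 7, two-sided 0.025 (z = 2.241) and 20% loss, power = Φ(δ / [7√(2/n)] − 2.241).

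- H1: n = 282 × 0.8 / 2 = 112.8 per arm. SE = 7√(2/112.8) = 0.932. 2.90/0.932 = 3.111. Power = Φ(0.870) = 0.808.
- H2: n = 250 × 0.8 / 2 = 100 per arm. SE = 0.990. 3.07/0.990 = 3.101. Power = Φ(0.860) = 0.805.

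Both agree with the stated 80%.

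**Step 2. Simulate trials in which sessions have no effect.**

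- From the documents: 113 analysed per arm (112.8 rounded), baseline 13 cigarettes/day (SD 7), five stage-1 sessions, and 12-week abstinence of 16% (NRT+CM) and 7% (NRT), as assumed in the original calculation in section 9.2.
- Assumed: smoking participants attend 65% of visits. In the CM arm only, attendance while abstinent is higher by 0, 10, 20 or 30 points. Week-12 quitters are abstinent at 80% of visits and others at 5% (weaker persistence: 50% and 10%). Continuing smokers average about 75% of baseline consumption. The test is two-sided at 0.05.
- Models: linear regression of week-12 cigarettes/day on session count, arm and baseline consumption; logistic regression of abstinence on session count and arm. 1,500 runs per setting.

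Percentage of runs in which session count is significant:

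| Attendance gap (points) | Cigarettes/day | Abstinence | Cigarettes/day, weaker persistence | Abstinence, weaker persistence |
|---|---|---|---|---|
| 0 | 4 | 5 | – | – |
| 10 | 11 | 19 | 6 | 9 |
| 20 | 27 | 64 | 11 | 21 |
| 30 | 48 | 92 | 19 | 45 |

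A simpler model, with each participant's abstinence fixed throughout and 11.5% abstinent in both arms, gives 22% and 61% at a 20-point gap in the CM arm only. That is close to the 27% and 64% above.

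**Step 3. Size of the spurious slope.** With the stronger persistence, the average slope is −0.22, −0.44 and −0.66 cigarettes/day per session at gaps of 10, 20 and 30 points. At 20 points, going from none to all five sessions gives 5 × 0.44 = 2.2 cigarettes/day of apparent benefit. The trial's detectable H1 difference is 2.90.

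**Step 4. Where the payment route acts.** In the NRT arm alone the cigarettes/day test rejects about 5% of the time at every gap. In the CM arm alone it falsely shows a benefit in 14%, 42% and 74% of runs (nominal 2.5% in that direction).

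**Step 5. Add shared motivation.** With a 20-point gap and a motivation loading of 0.2 or 0.3, the pooled cigarettes/day test rejects 55% or 87% of the time, and the NRT arm alone 9% or 28%.

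**Step 6. Can adjustment rescue the causal reading?** Adjusting for abstinence at every visit, assumed known even when the visit was missed, returns the rate to 4–6% if payment is the only cause. With motivation added it remains at 11% (loading 0.2) or 34% (loading 0.3).

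**The case against.** The item is one sentence under an exploratory heading. It states no null hypothesis and specifies no test, so the false-positive rates belong to a conventional 0.05 test supplied here. It also carries a literature reference whose entry is not in the text available, and a method may be given there. All of this stands and limits the weight of the point. It does not make a self-selected count a randomized dose.

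A reader might infer that the analysis will often show a false dose response. The documents do not support that. They give no attendance data, and even the direction of the gap is assumed: quitters might attend less once they have quit, which would reverse the bias. With weaker persistence of abstinence the rate for cigarettes/day is only 6% to 19%. Much higher rates appear if the gap is applied to both arms (in the simpler model, 68% for cigarettes/day at 20 points). But NRT-only participants receive no CM in stage 1, so in that arm payment cannot be the cause and another, such as motivation, is needed.

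A reader might also infer that a false result would feed straight into Aim 3. As described in sections 2.1 and 2.2, Aim 3 rests on recruitment experience, staff surveys, costs and participant satisfaction. It poses no question about how many sessions to offer.

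**Conclusion.** The concern holds as a point about interpretation. Session count is not randomized, is chosen after randomization, and in CM participants can be a result of abstinence, so the analysis supports only a statement of association. It can show a benefit of sessions when there is none.

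How often depends on assumptions the documents cannot settle. The ranges of roughly 6–48% for cigarettes/day and 9–92% for abstinence rest on five sessions, 65% attendance while smoking, a gap of 10 to 30 points in CM participants only, and the two persistence patterns tried. H1 and H2 compare randomized groups and are untouched. This is a low-cost correction to an exploratory analysis, worth making because it changes what the trial may conclude from it.

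**What to change.** Replace the sentence in section 9.4.8 with:

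> We will describe the association between number of completed sessions and outcomes. Only sessions held before the outcome assessment will be counted, visits credited by informant attestation will not be counted as attended sessions, and results will be presented separately by CM status. Because attendance is not randomized and may be a consequence of abstinence, results will be reported as associations with attendance and not as a dose response or an effect of intervention intensity.

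For week 24, the text should also say how participants who receive CM only from stage 2 are classed. Presenting results by CM status shows where the payment route can act but does not remove the bias (step 4), so the labelling is the part that protects the conclusion.

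An instrumental-variable model with randomized arm as the instrument is not a good substitute. Arm does not assign the number of visits, so the exposure would have to become CM sessions. The estimate would essentially be the H1 difference divided by mean CM sessions attended. It would also require that CM acts only through completed sessions, although the prospect of prizes could change smoking without one.

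The cost is a text edit using data already collected. The trial gives up a causal dose-response statement it could not support, and loses a little precision by reporting within CM status.

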10 SUPPORTING DOCUMENTATION AND OPERATIONAL CONSIDERATIONS

10.1 REGULATORY, ETHICAL, AND STUDY OVERSIGHT CONSIDERATIONS

10.1.1 INFORMED CONSENT PROCESS

Where and When Consent Will Be Obtained

For aims 1 and 2, patients will be consenting in person in the clinic where they have been recruited from or remotely. Due to social distancing requirements and safety protocols, if the situation requires, participant may be consented via phone or HIPAA compliant video conferencing with Zoom. Participants can either mail the signed consent or bring back a signed copy in person within two weeks of the phone call/video call or email it to research assistant.

For aim 3, for the survey, clinicians, staff, clinical leadership, social workers, psychologists, and care coordinators will be located wherever they have access to email and the online REDCap survey. They will not be providing any health identifiers and thus there will be no need for HIPAA authorization. They will only need to provide consent prior to study activities. The consent document will be located on the very first page of the survey; participants will not be allowed to proceed unless they agree to the terms of consent.

Waiting Period for Obtaining Consent

Participants will have as much time as needed to thoroughly review the consent form.

10.1.1.1 CONSENT/ASSENT AND OTHER INFORMATIONAL DOCUMENTS PROVIDED TO PARTICIPANTS

Script for public service announcement (SUNY Downstate site only)
MyChart script change (Yale site only)
Recruitment letter change (Yale site only)
Letters for participants lost to follow up (all sites)

10.1.1.2 CONSENT PROCEDURES AND DOCUMENTATION

Informed consent is a process that is initiated prior to the individual's agreeing to participate in the study and continues throughout the individual's study participation. Consent forms will be Institutional Review Board (IRB)-approved and the participant will be asked to read and review the document. The investigator will explain the research study to the participant and answer any questions that may arise. A verbal explanation will be provided in terms suited to the participant's comprehension of the purposes, procedures, and potential risks of the study and of their rights as research participants. Participants will have the opportunity to carefully review the written consent form and ask questions prior to signing. The participants should have the opportunity to discuss the study with their family or surrogates or think about it prior to agreeing to participate. The participant will sign the informed consent document prior to any procedures being done specifically for the study. Participants must be informed that participation is voluntary and that they may withdraw from the study at any time, without prejudice. A copy of the informed consent document will be given to the participants for their records. The informed consent process will be conducted and documented in the source document (including the date), and the form signed, before the participant undergoes any study-specific procedures. The rights and welfare of the participants will be protected by emphasizing to them that the quality of their medical care will not be adversely affected if they decline to participate in this study.

10.1.2 STUDY DISCONTINUATION AND CLOSURE

This study may be temporarily suspended or prematurely terminated if there is sufficient reasonable cause. Written notification, documenting the reason for study suspension or termination, will be provided by the suspending or terminating party to study participants, investigator, funding agency, and regulatory authorities. If the study is prematurely terminated or suspended, the Principal Investigator (PI) will promptly inform study participants, the Institutional Review Board (IRB), and sponsor and will provide the reason(s) for the termination or suspension. Study participants will be contacted, as applicable, and be informed of changes to study visit schedule.

Circumstances that may warrant termination or suspension include, but are not limited to:

- Determination of unexpected, significant, or unacceptable risk to participants
- Demonstration of efficacy that would warrant stopping
- Insufficient compliance to protocol requirements
- Data that are not sufficiently complete and/or evaluable
- Determination that the primary endpoint has been met
- Determination of futility

Study may resume once concerns about safety, protocol compliance, and data quality are addressed, and satisfy the sponsor and IRB.

10.1.3 CONFIDENTIALITY AND PRIVACY

Participant confidentiality and privacy is strictly held in trust by the participating investigators, their staff, and the sponsor(s) and their interventions. This confidentiality is extended to cover testing of biological samples in addition to the clinical information relating to participants. Therefore, the study protocol, documentation, data, and all other information generated will be held in strict confidence. No

information concerning the study or the data will be released to any unauthorized third party without prior written approval of the sponsor.

All research activities will be conducted in as private a setting as possible.

The study monitor, other authorized representatives of the sponsor, representatives of the Institutional Review Board (IRB) or other regulatory agencies may inspect all documents and records required to be maintained by the investigator, including but not limited to, medical records (office, clinic, or hospital) and pharmacy records for the participants in this study. The clinical study site will permit access to such records.

The study participant's contact information will be securely stored at each clinical site for internal use during the study. At the end of the study, all records will continue to be kept in a secure location for as long a period as dictated by the reviewing IRB, Institutional policies, or sponsor requirements.

Study participant research data, which is for purposes of statistical analysis and scientific reporting, will be transmitted to and stored at the Yale Coordinating Center. This will not include the participant's contact or identifying information. Rather, individual participants and their research data will be identified by a unique study identification number. The study data entry and study management systems used by clinical sites and by the Yale Coordinating Center research staff will be secured and password protected. At the end of the study, all study databases will be de-identified and archived at the Yale Coordinating Center.

Certificate of Confidentiality

To further protect the privacy of study participants, a Certificate of Confidentiality will be issued by the National Institutes of Health (NIH). This certificate protects identifiable research information from forced disclosure. It allows the investigator and others who have access to research records to refuse to disclose identifying information on research participation in any civil, criminal, administrative, legislative, or other proceeding, whether at the federal, state, or local level. By protecting researchers and institutions from being compelled to disclose information that would identify research participants, Certificates of Confidentiality help achieve the research objectives and promote participation in studies by helping assure confidentiality and privacy to participants.

